the location of the fracture. The appropriate region will be prepped with a chlorohexidine solution on the appropriate surgical side and the appropriate site will be visualized under ultrasound. For the group receiving a single shot block, a 22 gauge, 3.5 inch needle will be used and 20cc of 2% lidocaine with 1:200,000 epinephrine + 20 cc of 0.5% bupivacaine with 1:300,000 epinephrine will be injected around the nerve after confirming negative aspiration every 5 cc. For those receiving a continuous infusion, a 17 gauge Tuohy needle will be used and 20cc of 2% lidocaine with epinephrine + 20 cc of 0.5% bupivacaine with 1:300,000 epinephrine will be injected around the nerve after confirming negative aspiration every 5cc. Once the injection is complete, an indwelling catheter will be placed with its tip location confirmed and then secured at the skin.

After placement of the regional block, general anesthesia/sedation will be administered and maintained at the discretion of the anesthesiologist. Induction of anesthesia will involve IV propofol (2mg/kg) and fentanyl (1-2mcg/kg). Neuromuscular blockade will be used at the discretion of the anesthesiologist and will be reversed appropriately. Anesthetic maintenance will involve inhalational agents, IV agents, air, and oxygen. Fentanyl will be the only intraoperative analgesic used and will be dosed as determined by the anesthesiologist.

After completion of the surgery, patients will be taken to the PACU where those with continuous catheters will have an OnQ pump attached to it. The patient will begin receiving a continuous infusion of 0.2% ropivacaine through the catheter at a rate of 8 cc/hr. The patient will be discharged home with the catheter for 48 hours. The study participant will self-discontinue the catheter in 2 days. This involves removing the tegaderm dressing and gently pulling the catheter out from under the skin. A bandage may then be applied. [name], our anesthesiology RN, will be available via phone to answer any questions study participants may have regarding discontinuation of the catheter. Breakthrough pain while in the PACU will be treated with IV fentanyl and PO Percocet as needed.

Postoperatively, all patients will be discharged home with a prescription for Percocet 5/325 with instructions to take 1-2 tabs every 4-6hrs as needed for pain.

Data collection

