Location and type of surgical procedure, duration of procedure, and duration of intravenous sedation will also be recorded. Total time in the operating room will also be noted. Time admitted to PACU, time clinically ready for discharge, time actually discharge, PACU medications for nausea/vomiting and PACU meds for pain will all be recorded prior to discharge.

Post-operative pain will be assessed using the Visual Analogue Scale (0-100) prior to being discharged from PACU. Time to discharge and amount of pain medication taken in the PACU will be recorded.

Patients will be contacted 8 hours, 12 hours, 24 hours, 48 hours and 72hrs after surgery by the operative surgeon or research coordinator to assess their pain scale and pain medication intake. Patients will be seen for routine post-operative follow-up visits at two, six, twelve, twenty-four, and fifty-two weeks. At these times, patients will be assessed for pain, residual neurological symptoms, and signs of infection. Patients will also be asked if they were satisfied with their postoperative pain control. Total duration of study will be fifty-two weeks. Data collection documents will be distributed to the patients at time of surgery to assist in patient understanding.

Inclusion criteria

1. Patients at least 18 years old.
2. Male or Female
3. All racial and ethnic groups
4. Fractures and fracture/dislocations of the foot, ankle, tibia, fibula, elbow, forearm, wrist and hand
5. Patients who opt for surgical treatment of their fractures.
6. Patients who consent to be randomized.
7. Patients who are willing to follow-up for a minimum of 52 weeks.

Exclusion criteria

1. Patients younger than 18 years old.
2. Patients who are on chronic opioids
3. Patients who abuse opioids
4. Patients who are unwilling to follow-up for a minimum of 52 weeks.
5. Neurologic condition that could interfere with pain sensation

Characteristics of the Research Population

1. **Total number of subjects:** 100 subjects
2. **Gender:** Male or Female
3. **Racial and Ethnic Origins:** All are included

Study payments/cost:

Study participants will not incur any additional costs or payments as a result of this study. Any additional costs will be absorbed by the NYU Departments of Orthopaedics and Anesthesia

Potential Risks and Discomforts:

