2. Responsibilities and roles for gathering, evaluating and monitoring the data:
 - a. All data (including details about adverse/unexpected events) will be collected by the operative team or research coordinator at specific time points: 8hrs post-op, 24hr, 48hr, 72hrs, 2wks, 6wks, 12wks, 24wks and 52wks and reported to the research coordinator using standard templated data collection forms. All patients will be told to call [name] at [contact] to report adverse reactions during the study.
 - b. All data will be verified by the research team and coordinator for accuracy and compliance with the protocol at each time point as designated above.
3. Information about the monitoring entity:
 - a. Principle investigator [name], [name], and [name] comprise the monitoring entity.
4. Reporting Adverse events and Unanticipated problems to the monitoring entity:
 - a. The Principal Investigator will submit a Reportable Events Form for all reportable information to the IRB within 5 working days from when the Principal Investigator learns of the event or new information.
5. Assessments:
 - a. The Monitoring entity will review data monthly and assess the data for unanticipated problems involving risks to participants.
6. Criteria for Action:
 - a. Specific triggers for action include any event that is deemed to be a risk to life or limb.
7. Procedure for communicating:
 - a. The Principal Investigator will submit a Reportable Events Form for all reportable information to the IRB within 5 working days from when the Principal Investigator learns of the event or new information.

Data Storage and Confidentiality: All patients will be de-identified and given a code. Information linking the linkage codes to the participants' names, social security numbers and medical record numbers will be stored in a secure location separate from the medical information. Access to the information linking the linkage codes with participant identifiers shall be documented. The patient's informed consent will be obtained in one of the exam rooms in the private office.

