Participant medical information will be stored electronically within a password protected spreadsheet available only to the PI, co-investigators, and research staff as necessary for data analysis. The names, social security numbers, and medical record numbers of the study participants will be deleted from their stored medical information and replaced with a linkage code. Access to participant medical information contained within the registry will be restricted.

Protection Against Risk: All procedures will be performed as outlined above. After the procedure pt will be contacted 6-8 hours after surgery and at 24 hours, 48 hours and 72hours after surgery by the operative surgeon or research coordinator to assess their pain scale and pain medication intake. Patients will be seen for routine post-operative follow-up visits at two, six, twelve, twenty-four, and fifty-two weeks. At these times, patients will be assessed for pain, residual neurological symptoms, and signs of infection, and starting at the six week time point, patient's functional status will be assessed using the Disability of the Arm, Shoulder and Hand (DASH) and SMFA scores, both are widely accepted and validated functional measures.

Method of Subject Identification and Recruitment: All patients seen in the outpatient office, who fit the inclusion criteria will be asked to participate in the study.

Subject/Representative Comprehension: None

Debriefing Procedures: All patients will have regular follow-up at which point, all questions regarding the study can be answered.

Documentation of Consent: A copy of the signed consent form will be securely kept for our records.

Statistical analysis plan:

A preoperative power analysis was performed. On a VAS scaled from 1-100, assuming a standard deviation of 20, the number needed to detect a 10 point change in VAS was 38. Assuming a drop out rate of 20%, we will require 50 patients in each group to determine significance. The primary end points of the study for Visual Analog Score will be assessed using two-group t-tests (Mann-Whitney U test where appropriate). Amount of pain medication utilized post operatively will be assessed using Student t-tests. Residual neurological symptoms and signs of infection will be reported as descriptive statistics. Descriptive statistics will be reported as means +/- SD for continuous variables and as frequencies and percentages for categorical variables.

References

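### The operating surgeon or team may collect the 8–72 h pain and medication outcomes with no masking, which adds a reducible interviewer component to a subjective, open-label endpoint

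*Combined protocol and SAP*

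**What the plan says.** Three places in the combined protocol and SAP say who gathers the early outcomes.

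- **Data collection:** patients are contacted at 8, 12, 24, 48 and 72 hours "by the operative surgeon or research coordinator to assess their pain scale and pain medication intake".
- **Protection Against Risk:** the same two roles are named, with contacts at 6–8, 24, 48 and 72 hours.
- **Data Monitoring Plan, item 2a:** "All data (including details about adverse/unexpected events) will be collected by the operative team or research coordinator at specific time points". This covers the early contacts (12 hours is not listed), the visits to 52 weeks, and adverse events.

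On visibility of the arm, the Intervention section says that in the PACU "those with continuous catheters will have an OnQ pump attached to it", and later that "The study participant will self-discontinue the catheter in 2 days". It describes no sham catheter or pump for the single-shot arm. No section describes masking of patient, surgeon, coordinator or assessor.

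On use of the data, the Statistical analysis plan says "The primary end points of the study for Visual Analog Score will be assessed using two-group t-tests", without naming a time point, and "Amount of pain medication utilized post operatively will be assessed using Student t-tests".

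Two partial safeguards appear. Item 2 of the Data Monitoring Plan calls for templated forms and for verification of the data at each time point. Data collection adds that "Data collection documents will be distributed to the patients at time of surgery to assist in patient understanding".

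**The concern.** A VAS score is the patient's own rating, but here it reaches the record through a conversation. A patient may answer the surgeon who operated differently from a coordinator, and a caller who knows the allocation may prompt differently. Either effect distorts the comparison if it differs between arms.

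The plan allows two kinds of caller and gives no rule for choosing between them. It does not require the same kind in both arms, and it describes no script. The medication count is exposed in the same way.

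The patient's own knowledge of the arm can hardly be removed without a sham. The interviewer part can be reduced with resources the plan already has. A larger sample would not help: it narrows the standard error around a biased difference.

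**Working it through.** **1. Can the surgeon be expected to know the arm?** The documents do not say so outright. It follows from an indwelling catheter in one arm only, a pump attached in the PACU and taken home, no sham, and no masking text. Contact by phone is likewise an inference: the text says only that patients are contacted, but they have been discharged home.

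**2. Do the stated safeguards cover it?** Templated forms standardise what is written down, and verification checks the record. Neither governs who asks or what the asker knows. The patient-held documents are described as an aid to understanding, not as a self-completed source record.

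**3. The plan's figures.** The plan gives no figure for interviewer bias. Its sample-size paragraph supplies SD 20, a 10-point target, 38 needed, 20% dropout and 50 per group.

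- The dropout step roughly reproduces: 38 / 0.8 = 47.5, so 48, against 50.
- The 38 does not follow from SD 20 and 10 points at usual settings. A two-sided 5% test with 80% power needs 2 × (1.960 + 0.842)² × 20² / 10² = 62.8, so 63 per group. Alpha and power are not stated. This is a separate matter and does not affect the present point.
- Evaluable patients per arm used below: 50 × 0.8 = 40.

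**4. What a net shift would do (illustration).** Assume no true effect, two-sided alpha of 5%, and a net between-arm reporting shift b. The values of b are assumptions.

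SE = 20 × √(2/40) = 4.47 points.

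Type I error = Φ(−1.96 − b/SE) + 1 − Φ(1.96 − b/SE).

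| b (VAS points) | b / SE | Share of 10-point target | Type I error |
|---|---|---|---|
| 0 | 0 | 0% | 5.0% |
| 1 | 0.22 | 10% | 5.6% |
| 2 | 0.45 | 20% | 7.3% |
| 3 | 0.67 | 30% | 10.3% |
| 5 | 1.12 | 50% | 20.1% |

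The noncentral t distribution gives nearly the same values: 7.3%, 10.2% and 19.7% for 2, 3 and 5 points. For shifts of 2 to 5 points, the normal formula gives 7.2–19.3% with 38 per arm (SE 4.59) and 7.9–24.0% with 50 per arm (SE 4.00).

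**5. What would produce such a shift through the mix of callers?** By this route,

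bias = (difference in reporting to surgeon versus coordinator) × (difference between arms in the share of surgeon contacts).

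With an assumed reporting difference of 10 points, a 2-point bias needs a caller imbalance of 2/10 = 20 percentage points, and a 5-point bias needs 5/10 = 50. If the caller is chosen without regard to arm, the second factor is zero in expectation, and so is the bias. The other route, arm-dependent prompting, has no figure in the documents.

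**The case against.** The strongest reply is that the mechanism is speculative. The same contact times apply to all patients, and nothing in the documents suggests that the choice of caller depends on arm. The size of the shift is assumed, and any assumed shift would yield a table like the one above. Patients know their arm and would still know it after the change. The coordinator is not stated to be masked, so one unmasked caller might replace another. All of this stands. It limits the point to a cheap improvement, but it does not justify leaving the choice of an allocation-aware treating clinician open.

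A reader might infer more than the documents support:

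- **That the surgeon would call pump patients more often because of catheter questions.** The Intervention section assigns phone questions about catheter removal to an anesthesiology nurse.
- **That the caller's identity goes unrecorded, so no analysis could examine it.** The protocol is silent. The templated forms are not shown and may include it.
- **That the primary score is one of these contact scores.** No primary time point is named, and a VAS is also taken before PACU discharge by an unnamed person. Medication amount is tested but not called primary.

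**Conclusion.** The point holds as a cheap improvement. The plan lets the operating surgeon or team elicit the 8–72 h pain scores and medication intake, without masking and with the arm evident from the catheter and pump. This adds an interviewer component that could be reduced.

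Neither its size nor its direction can be taken from the documents. The 7–20% range is conditional on an assumed net shift of 2 to 5 points, SD 20, 40 per arm and a two-sided 5% test; at 1 point the effect is slight (5.6%). It should not be read as the trial's actual false-positive rate. The word avoidable applies only to the interviewer's contribution, not to the patient's knowledge of the arm.

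**What to change.** Amend Data collection and Protection Against Risk, and amend Data Monitoring Plan item 2a only for the 8–72 h pain and medication outcomes:

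1. The research coordinator, not the surgeon or operative team, makes the outcome contacts in both arms.
2. One fixed script asks for the pain score and tablet count before anything else. The call sheet does not show the allocation.
3. At each time point, before the contact, the patient writes the VAS and tablet count on the data collection documents already handed out. That entry is the source record. This step matters most, because it takes the interviewer out of the score even if the coordinator learns the arm.
4. The form records who made the contact.

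Adverse-event reporting and safety contacts by the surgical team stay as they are, kept separate from outcome collection.

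The cost is small but goes beyond wording: a short script, a call sheet and form fields. The coordinator takes on contacts the surgeon would otherwise have made, up to 100 patients × 5 contacts = 500, some at 8 and 12 hours. Cover for those hours should be arranged so that the change does not create missing data. Sample size, treatment and visit schedule are unchanged.

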All patients being treated with open reduction internal fixation for foot, ankle, tibia, elbow, forearm and wrist fractures at New York University Medical Center, NYU-Hospital for Joint Diseases will be asked to participate in this study. At the patients preoperative office visit, they will be asked to participate in the study and provided a copy of the consent form at that time which they can take home with them. All questions will be answered and they will be asked verbally if they will consent to being a part of the study. Patients will then have the opportunity to either sign the written consent forms or wait till the surgical date to think about the study and any additional questions they may have. At the time of surgery, patients will be consented for surgery. If the patient did not give written consent at the preoperative visit, they will be asked if they have any questions about the study. All questions will again be answered. They will then be asked verbally if they are willing to participate in the study, if they respond yes, then written consent will be obtained at that time.

Randomization

Patients will then be randomized (using an online randomizer, similar to a flip of a coin) to one of two anesthetic protocols: regional block with single dose of anesthetic versus regional block with continuous infusion using an OnQ pump. If for some reason, the anesthesiologist feels that a patient would benefit from one type of anesthesia over another, the patient will be removed from the study and given that type of anesthesia.

Intervention

Patients will be randomized to one of two anesthetic protocols: general anesthesia/sedation with a single shot, peripheral nerve block versus general anesthesia/sedation with a continuous, peripheral nerve block.

All anesthesia will be provided by an attending anesthesiologist with or without an anesthesiology resident/CRNA. Patients will have standard ASA monitors placed (pulse oximeter, blood pressure, EKG) and an intravenous line started. Sedation will be given using a combination of midazolam (1-4 mg) and fentanyl (25-100 mcg). Patients in both groups will receive an ultrasound-guided peripheral nerve block. The block will be either an infraclavicular brachial plexus block or a popliteal nerve block, depending on

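### Short-term opioid use before surgery is neither excluded nor listed for recording, so the unadjusted comparison of postoperative pain medication gives up some precision and cannot be checked for chance imbalance

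*Combined protocol and SAP*

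**What the plan says.** **Eligibility.** Under Exclusion criteria, item 2 reads "Patients who are on chronic opioids" and item 3 reads "Patients who abuse opioids". No item deals with a short course of opioids taken for the injury itself.

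**Data.** The surgical items under Data collection are these: "Location and type of surgical procedure, duration of procedure, and duration of intravenous sedation will also be recorded". For medication, the same section states "Time to discharge and amount of pain medication taken in the PACU will be recorded", and after discharge "Patients will be contacted 8 hours, 12 hours, 24 hours, 48 hours and 72hrs after surgery". The Data Monitoring Plan has data gathered at "specific time points: 8hrs post-op, 24hr, 48hr, 72hrs, 2wks, 6wks, 12wks, 24wks and 52wks". All of these medication and monitoring time points fall after surgery. A preoperative office visit takes place, but the Consent section describes it only for recruitment and consent.

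**Allocation.** Randomization is done "using an online randomizer, similar to a flip of a coin", and no stratification factor is stated.

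**Analysis.** The Statistical analysis plan says "Amount of pain medication utilized post operatively will be assessed using Student t-tests". It names no covariate. The same section gives primary status to the VAS and bases the sample size on the VAS alone.

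**The concern.** These patients have fractures and are seen in the office before a surgical date, so there is an interval in which some may plausibly take opioids for the injury. The medication outcome is as needed: the discharge prescription described under Intervention permits anything from none to 36 tablets over 72 hours (at most 2 every 4 hours, so 2 × 72/4). Much of the spread will therefore come from patient behaviour, and earlier use of the same class of drug is a natural baseline covariate.

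If that covariate is not collected, three things follow. The report cannot show whether the arms were alike on it. The analysis cannot adjust for it. Any precision that adjustment would bring is forgone, in an outcome for which the trial was not sized. A baseline answer is also hard to recover reliably afterwards, and an adjustment chosen once the data are in is less credible than one set in advance.

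**Working it through.** **1. The plan's own figures.** The documents give no SD, target difference or sample size for medication intake. The only figures are for the VAS: 38, then 20% dropout, then 50 per group. The dropout step gives 38/(1 − 0.20) = 47.5, so 48, close to the 50 chosen. (The 38 itself is not what the usual two-sided two-sample formula gives for a 10-point difference and SD 20 at 80% power: 2 × (1.960 + 0.842)² × 20²/10² = 62.8, so 63 per arm. That is a separate matter and is not used here.) For this point, evaluable patients per arm = 50 × (1 − 0.20) = 40.

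**2. Is the covariate available?** Setting the exclusions beside the data lists, short-term preoperative opioid use is allowed in but not listed for recording. Days since injury is not listed either.

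**3. How far could the arms differ by chance?** Let p be the share with preoperative opioid use (assumption; the documents give none) and n the number per arm, taken as equal. The 95% range for the difference in shares is ±1.96 × √(p(1 − p) × 2/n).

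| p | 40 per arm | 50 per arm | Chance of a gap of 10 points or more (40 / 50 per arm) |
|---|---|---|---|
| 0.2 | 17.5 points | 15.7 points | 26% / 21% |
| 0.3 | 20.1 points | 18.0 points | 33% / 28% |
| 0.5 | 21.9 points | 19.6 points | 37% / 32% |

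The range at p = 0.7 equals that at p = 0.3.

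**4. What would adjustment gain?** Let r be the correlation of preoperative with postoperative use (assumption). Adjustment multiplies residual variance by 1 − r², so 40 per arm performs like 40/(1 − r²). The detectable difference at two-sided 5% and 80% power is (1.960 + 0.842) × √(2/40) × √(1 − r²) in SD units.

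| r | Variance removed | Equivalent n per arm | Detectable difference (SD) | Power for 0.5 SD |
|---|---|---|---|---|
| 0 (unadjusted) | 0% | 40 | 0.63 | 61% |
| 0.2 | 4% | 42 | 0.61 | 63% |
| 0.3 | 9% | 44 | 0.60 | 65% |
| 0.4 | 16% | 48 | 0.57 | 68% |
| 0.5 | 25% | 53 | 0.54 | 73% |

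**5. Are steps 3 and 4 two harms or one?** Suppose prior users take d more tablets than others. At the 95% limit of imbalance the arm difference shifts by d × 1.96 × √(p(1 − p) × 2/n). The half-width of the unadjusted 95% CI is 1.96 × SD × √(2/n). The ratio is d√(p(1 − p))/SD, which for a yes/no covariate is r. For example, with p = 0.5, d = 6 and r = 0.3 (assumptions), SD = 6 × 0.5/0.3 = 10 tablets, the shift is 0.219 × 6 = 1.3 tablets, and the half-width is 1.96 × 10 × √0.05 = 4.4 tablets: 1.3/4.4 = 0.30. The shift is thus already inside the sampling error that the t-test reports. It is one loss, seen from two sides.

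**The case against.** The strongest reply is that a randomized comparison needs no baseline covariate. Chance imbalance in any variable, measured or not, is already in the t-test's standard error, and adjusting an outcome that is not primary is good practice but optional. This stands, and it limits the point to precision and description.

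Three further parts of the reply also stand.

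- Nothing in the documents shows that prior opioid use is the strongest predictor of later use, or how many patients will have taken any. A reader might infer the former; only a range can be given.
- The lists do not claim to be complete, and the Data Monitoring Plan refers to templated collection forms that are not part of the documents. Applying exclusions 2 and 3 also means asking about opioids in some form. So the supportable statement is that acute use is not listed for recording, not that it will never be recorded.
- Using 40 per arm is cautious. The 20% dropout has no time point in a 52-week study, and the medication contacts end at 72 hours. With 50 per arm, the same correlations of 0.3 to 0.5 give an equivalent 50/0.91 = 55 to 50/0.75 = 67. The relative gain does not change.

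What does not stand is that there is therefore nothing to do. A covariate that costs two questions, and a model that replaces a t-test, improve the analysis without an added visit or procedure.

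**Conclusion.** The point holds as a modest, inexpensive improvement. Short-term preoperative opioid use is neither excluded nor listed for recording, and the medication outcome is compared without adjustment. The cost is lost precision and no means of describing or adjusting for chance imbalance. For an assumed correlation of 0.3 to 0.5 the loss is 9% to 25% of residual variance, about 44 to 53 instead of 40 per arm. At 0.2 it is 4%, which is small.

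Two stronger readings are tempting, and the documents do not support them.

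- A reader might infer that the opioid comparison is biased or invalid. It is not: under randomization the unadjusted difference is unbiased in expectation. This assumes that the randomized groups stay intact. The Randomization section lets the anesthesiologist remove a patient without saying whether that can happen after allocation; that is a different issue.
- A reader might infer that only chronic users are kept out. Item 3 also excludes opioid abuse.

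The share of prior users and the correlation are assumptions throughout, and medication intake is not named as a primary end point.

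**What to change.** 1. On the day of surgery, before allocation, record the opioid tablets taken in the previous 24 hours (or yes/no) and the days since injury. Consent is the wrong moment for the 24-hour question, because the Consent section lets patients sign at the earlier office visit. State that allocation is drawn after the answers are recorded.
2. Show both items by arm in the baseline table.
3. In the SAP, replace the Student t-test for medication with a prespecified linear model of total opioid intake from PACU to 72 hours, expressed in one common opioid unit so that PACU and discharge medication can be added. Regress it on arm and preoperative opioid use, with robust standard errors, and report the adjusted difference with its 95% CI.

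The cost is two questions, the baseline-table rows and a short SAP change, with no extra visit, staff or procedure. The downside is that self-reported use is imprecise, and the gain will be small if the correlation proves low.

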The research-related complications associated with regional block include, but are not limited to, intravascular injection, local anesthetic toxicity, hematoma formation around insertion site, infection around injection site, permanent or temporary nerve injury, and allergic reactions to the medication injected.

The research-related complications associated with the On-Q pump include, but are not limited to, site infection, superficial nerve injury, and local anesthetic toxicity. There may be additional risk of injury in the On-Q pump Group, if participants resume regular activities, prematurely, while free of pain.

There may be unknown risks/discomforts involved. Study staff will update all patients in a timely way on any new information that may affect the patients' health, welfare, or decision to remain in the study. If the patients have any questions or sustain any injury during the course of the research or experience any adverse reaction to one of the surgical treatments they will be informed during the process of obtaining informed consent that they should contact the Principal Investigator [name] at the following [contact].

In addition, if there is any Adverse Event that occurs during the study, then the Principal Investigator will make the IRB aware of this. The Principal Investigator will submit a Reportable Events Form for all reportable information to the IRB within 5 working days from when the Principal Investigator learns of the event or new information.

Potential Benefits: The patients are not likely to receive any direct benefit from their participation in this study aside from possible increased pain relief after operative fixation of their fracture. However, the patients' participation may help the investigators better understand the best post-operative pain protocol for extremity fracture fixation. In addition, the patients' participation may help the investigators better understand if there is any prolonged benefit to one post-operative treatment over the other, which could thereby give orthopaedic surgeons conclusive evidence of the best post-operative pain protocol for operative fractures about the forearm and wrist that could also translate into better patient satisfaction.

Data Monitoring Plan:

1. Types of data or events:
 - a. Intravascular injection
 - b. local anesthetic toxicity
 - c. hematoma formation
 - d. Infection
 - e. Neurologic injury
 - f. Allergic reaction

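### Injury from early return to activity, a possible added risk with the On-Q pump, has no entry in the monitored-event list, no prompt at follow-up and no by-arm summary in the SAP

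*Combined protocol and SAP*

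**What the plan says.** Potential Risks and Discomforts lists complications of the regional block and of the On-Q pump, then adds one risk described as possibly greater in one arm: "There may be additional risk of injury in the On-Q pump Group, if participants resume regular activities, prematurely, while free of pain".

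Data Monitoring Plan, item 1, follows with six event types: intravascular injection, local anesthetic toxicity, hematoma, infection, neurologic injury and allergic reaction. The only injury term is "e. Neurologic injury".

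Item 2a provides general collection: "All data (including details about adverse/unexpected events) will be collected by the operative team or research coordinator at specific time points". These are 8, 24, 48 and 72 hours and 2, 6, 12, 24 and 52 weeks, with findings "reported to the research coordinator using standard templated data collection forms". Patients are also told to contact the investigator if they "sustain any injury during the course of the research", and "if there is any Adverse Event that occurs during the study, then the Principal Investigator will make the IRB aware of this". On review, item 5 says: "The Monitoring entity will review data monthly and assess the data for unanticipated problems involving risks to participants".

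Data collection and Protection Against Risk describe the early telephone contacts as covering pain scores and pain medication. The clinic visits cover pain, neurological symptoms, infection and satisfaction with pain control, with DASH and SMFA from six weeks.

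On harms, the Statistical analysis plan has one sentence: "Residual neurological symptoms and signs of infection will be reported as descriptive statistics".

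**The concern.** The protocol foresees a specific harm, attaches it to one arm and gives a mechanism: a patient without pain does too much too soon. It then does not carry that harm into the event list, the described follow-up questions or the analysis. Pain questions are a poor substitute. On the protocol's own reasoning the injury happens while the patient is free of pain, so a low score during the 48-hour infusion is no reassurance.

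The trial hopes to tell surgeons which post-operative pain protocol is best (Potential Benefits). That judgement sets pain relief against harm. Pain is to be tested between arms. If the harm summary leaves out a foreseen pump-related risk, the balance is drawn from an incomplete account. An event not asked about at the time is also hard to recover afterwards.

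**Working it through.** The documents give no injury rate, so there is no figure of theirs to reproduce. The main check is textual.

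**Step 1. Named risks against Data Monitoring Plan, item 1**

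| Risk named in Potential Risks and Discomforts | Attached to | Entry in item 1 |
|---|---|---|
| Intravascular injection | Block | a |
| Local anesthetic toxicity | Block and pump | b |
| Hematoma | Block | c |
| Infection | Block and pump | d |
| Nerve injury | Block and pump | e |
| Allergic reaction | Block | f |
| Injury from premature activity | Pump (possible added risk) | none |

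Six of the seven map one to one. The activity-related injury is the only one without an entry.

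**Step 2. Is it asked about?** The described content of the calls is pain and medication. The described content of the visits is pain, neurological symptoms, infection, satisfaction and, from six weeks, function. None is a question on falls, activity or re-injury. Item 2a's general collection could record such an event if it came up. The templated forms themselves are not in the document, so this step rests on the protocol's description of them.

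**Step 3. Is it reported by arm?** The Statistical analysis plan covers neurological symptoms and infection only. It mentions neither other adverse events nor DASH and SMFA.

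**Step 4. What could the trial say about such an event if it were recorded?** Inputs from the Statistical analysis plan: 50 per arm and 20% dropout, so 50 × 0.80 = 40 remaining. All event rates below are assumptions.

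Exact two-sided 95% upper limit after zero events, 1 − 0.025^(1/n):
- n = 50: 1 − 0.025^(1/50) = 7.1%
- n = 40: 1 − 0.025^(1/40) = 8.8%

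Chance of at least one event in an arm, 1 − (1 − p)^n:

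| Assumed true rate p | n = 50 | n = 40 |
|---|---|---|
| 1% | 39% | 33% |
| 2% | 64% | 55% |
| 5% | 92% | 87% |
| 10% | 99.5% | 98.5% |

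Power of a two-sided 5% Fisher exact test:

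| Assumed rates | 50 per arm | 40 per arm |
|---|---|---|
| 2% v 5% | 2% | 1% |
| 2% v 10% | 19% | 11% |
| 5% v 15% | 24% | 18% |
| 2% v 20% | 78% | 64% |

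So events at a few per cent would probably be seen if asked about, and tabulating them is worthwhile. A significance test would be informative only for a very large difference.

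**The case against.** The strongest reply is that the plan does have a route for this event. Item 2a collects adverse and unexpected events from every patient, in both arms, at nine time points on standard forms. Patients are told to report any injury, and adverse events go to the IRB. DASH and SMFA might show a lasting injury. The action trigger in item 6, a threat to life or limb, is not confined to the six listed types. The risk itself is worded conditionally, as something that may occur.

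All of this stands, and it rules out three stronger readings that a reader might infer.

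- *That capture depends wholly on spontaneous reports, or that nobody would look.* Item 2a contradicts this. Collection is unspecific, not absent.
- *That the harm comparison is tilted towards the pump.* No between-arm test of harms is planned, and the general collection applies equally to both arms. The other named pump risks (infection, nerve injury and toxicity) are all on the list, and the two harms in the Statistical analysis plan relate to the first two of these.
- *That the monthly review would miss the event.* This is not shown. The narrower point is that the review looks for unanticipated problems, and an injury the protocol already foresees might not be classed as one.

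The reply does not fill the remaining gap. The event has no definition and no described prompt, and neither the general forms nor the IRB reports lead to a by-arm summary.

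**Conclusion.** The point holds as a gap in specificity and reporting. A harm that the protocol says may be greater with the pump is the only named risk missing from the monitored list. It is not prompted for in the described follow-up and has no place in the planned harm summary. That summary would be incomplete and, if the risk is real, could understate pump harm.

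The size cannot be given, because the documents state neither an injury rate nor how completely the general forms would capture it. The limits of 7.1% (0 of 50) and 8.8% (0 of 40) show how little reassurance a zero count would give for any event in this trial. They do not show that injuries will be missed.

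The conclusion assumes that the templated forms carry no injury question beyond what the protocol describes. If they already do, only the event list and the Statistical analysis plan need changing. The pain analysis is unaffected.

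**What to change.** 1. Data Monitoring Plan, item 1: add a seventh event, new injury, fall or re-injury of the operated limb, with a short definition. The sponsor should consider whether loss of fixation and reoperation belong within it.
2. Templated form: add one question on this event, worded identically for both arms and asked at the existing item 2a time points, at least through the early visits. The 8, 24 and 48 hour contacts cover the infusion period.
3. Statistical analysis plan: report all listed events by arm as counts and percentages with exact 95% confidence intervals. Keep this descriptive, with no formal test, because power would be low.

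The cost is one line in the event list, one question at contacts already scheduled and one safety table. There are no added visits and no change to treatment or sample size. The only downside is slightly longer calls.
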